Appendix 6. Bayesian Logistic Regression Model

Determination of the highRP2D will be based on the posterior probability of DLT estimated by a 5-parameter BLRM with overdose control {Babb 1998, Neuenschwander 2008}.

Let $\pi_1[d_1]$ be the probability of DLT during the first 7 weeks of study therapy at dose level d_1 of idelalisib and $\pi_2[d_2]$ be the probability of DLT at dose level d_2 of BI 836826, under the assumption that there is no drug-drug interaction. Let $\pi_{12}[d_1, d_2]$ denote the probability of DLT when the combination of the 2 drugs are given at dose level of d_1 for idelalisib with dose level of d_2 for BI 836826. Additionally, the d_1^* and d_2^* denote a reference dose of idelalisib and BI 836826, respectively. The statistical model describing dose-toxicity relationship will have the following form:

$$\pi_1[d_1] = \frac{\exp(\log(\alpha_1) + \beta_1 \log(\frac{d_1}{d_1^*}))}{1 + \exp(\log(\alpha_1) + \beta_1 \log(\frac{d_1}{d_1^*}))}$$

$$\pi_2[d_2] = \frac{\exp(\log(\alpha_2) + \beta_2 \log(\frac{d_2}{d_2^*}))}{1 + \exp(\log(\alpha_2) + \beta_2 \log(\frac{d_2}{d_2^*}))}$$

$$\pi_{12}^0[d_1, d_2] = \pi_1[d_1] + \pi_2[d_2] - \pi_1[d_1] \times \pi_2[d_2]$$

$$odds(\pi_{12}[d_1, d_2]) = \frac{\pi_{12}^0[d_1, d_2]}{1 - \pi_{12}^0[d_1, d_2]} \times \exp(\gamma [d_1 / d_1^*] \times [d_2 / d_2^*])$$

$$\pi_{12}[d_1, d_2] = \frac{odds(\pi_{12}[d_1, d_2])}{1 + odds(\pi_{12}[d_1, d_2])}$$

where

$$\alpha_1, \beta_1, \alpha_2, \beta_2 > 0, \text{ and } -\infty < \gamma < \infty$$

The prior specification of the model parameters is provided in Section 3. The estimate of parameters will be updated as data are accumulated and the toxicity probability at each dose level will be calculated based on the posterior distributions of the model parameters. The estimated posterior probability of DLT at each dose level will be summarized using the following intervals:

Under dosing: [0.00, 0.20)

Targeted toxicity: [0.20, 0.35)

Excessive toxicity: [0.35, 1.00]

The overdose control criterion is set as the posterior probability of excessive toxicity less than 25%. The maximum allowable dose increment for the subsequent cohort will be no more than 100% for each drug. Out of all dose candidates satisfying the overdose control criterion, the dose cohort at which the posterior probability for the target toxicity interval is the maximum will be chosen for the next dose cohort.

Dose search will continue until one of the following incidences occurs:

- Starting dose level is declared to be too toxic.
- Maximum number of subjects ($N = 36$) is reached.
- More than 6 subjects have been evaluated at this dose level, posterior probability of targeted toxicity exceeds 40% at this dose level, and a minimum of 12 subjects have been treated in total at all dose levels.

1. Planned Dose Levels

The provisional dose levels for idelalisib are 50 mg BID (starting dose), 100 mg BID, and 150 mg BID, and for BI 836826 are 100 mg (starting dose), 200 mg, and 400 mg. However, dose levels for BI 836826 may subsequently be modified to include additional doses through 600 mg, dependent on safety data from this study and from Boehringer Ingelheim study 1270.1.

2. Prior Specification

BLRM model parameters include (α_1, β_1) for idelalisib, (α_2, β_2) for BI 836826, and γ for interaction between idelalisib and BI 836826.

A bivariate normal prior distribution for $(\log(\alpha_1), \log(\beta_1))$ will be specified as follows:

- The estimated DLT rate at the reference dose (100 mg BID) will be set to 10%.
- Doubling the dose level is assumed to double the odds of DLT.
- Variance of $\log(\alpha_1)$ and $\log(\beta_1)$ are set to 2 with correlation of 0 to consider the uncertainty of priors.

A bivariate normal prior distribution for $(\log(\alpha_2), \log(\beta_2))$ corresponding to BI 836826 will be specified similarly as follows:

- The estimated DLT rate at the reference dose (200 mg BID) will be set to 10%.
- Doubling the dose level is assumed to double the odds of DLT.
- Variance of $\log(\alpha_2)$ and $\log(\beta_2)$ are set to 2 with correlation of 0 to consider the uncertainty of priors.

A normal prior will be specified for the interaction parameter γ as follows, in a way that the distribution reflects the uncertainty in safety profile by combining idelalisib with BI 836826.

- No increase/decrease in odds of DLT is expected by interaction of idelalisib and BI 836826.
- Variance of γ is set to 2 to consider the uncertainty of priors.

In summary, the parameters of the prior distributions for BLRM are provided in [Appendix Table 3](#), with the corresponding summaries of prior probability of DLT shown in [Appendix Table 4](#).

Appendix Table 3. Parameters of the prior distributions

Parameter	Means	Variiances	Correlation
Priors for idelalisib: $(\log(\alpha_1), \log(\beta_1))$	(-2.197, 0)	(2, 2)	0
Priors for BI 836826: $(\log(\alpha_2), \log(\beta_2))$	(-2.197, 0)	(2, 2)	0
Prior for interaction: γ	0	2	N/A

Appendix Table 4. Summary of prior probability of DLT

Dose level		Pr(DLT)	Prior Probability of		
Idelalisib	BI 836826	Median	Excessive [35%, 100%]	Target [20%, 35%]	Under [0%, 20%]
50 mg BID	100 mg	0.111	0.144	0.178	0.678
100 mg BID	100 mg	0.190	0.264	0.217	0.519
150 mg BID	100 mg	0.305	0.460	0.170	0.370
50 mg BID	200 mg	0.181	0.270	0.195	0.535
100 mg BID	200 mg	0.260	0.401	0.174	0.425
150 mg BID	200 mg	0.383	0.527	0.126	0.347
50 mg BID	400 mg	0.346	0.496	0.139	0.365
100 mg BID	400 mg	0.466	0.551	0.092	0.357
150 mg BID	400 mg	0.621	0.592	0.053	0.355

There are safety data available from Study 101-02 in which subjects with previously treated CLL received monotherapy idelalisib ([Appendix Table 5](#)) and from ongoing Phase 1 dose-escalation study 1270.1 in which subjects with R/R CLL received BI 836826 ([Appendix Table 6](#)). Assuming there is no drug-drug interaction, the predicted DLT probabilities of combination doses are summarized in [Appendix Table 7](#).

The proposed priors have higher probabilities of DLT than the predicted ones using historical data at each combination dose level. The study will use more conservative priors for the combination therapy.

Appendix Table 5. Summary of DLTs* from monotherapy idelalisib study

Dose of idelalisib	No of DLTs/No of evaluable subjects
100 mg BID	3/11
150 mg BID	8/52
200 mg BID	3/10
350 mg BID	3/7

* Number of DLTs is retrospectively re-calculated using the definition of DLT in Study GS-US-312-1579

Appendix Table 6. Summary of DLTs from monotherapy BI 836826 study

Dose of BI 836826	No of DLTs/No of evaluable subjects
1 mg	0/3
3 mg	0/3
9 mg	0/6
25 mg	0/6
50 mg	0/3
100 mg	0/3
200 mg	1/6
400 mg	0/3
800 mg	1/2

Appendix Table 7. Summary of DLTs predicted from monotherapy of Idelalisib and BI 836826

Dose level		Pr(DLT)
Idelalisib	BI 836826	Median
50 mg BID	100 mg	0.107
100 mg BID	100 mg	0.169
150 mg BID	100 mg	0.222
50 mg BID	200 mg	0.152
100 mg BID	200 mg	0.211
150 mg BID	200 mg	0.261
50 mg BID	400 mg	0.259
100 mg BID	400 mg	0.311
150 mg BID	400 mg	0.355

3. Operating Characteristics

In order to assess operating characteristics, simulation studies were performed under 2 hypothetical scenarios. A total of 1000 trials were simulated under each scenario.

- Scenario 1: Only lowest dose level is safe
- Scenario 2: Only 2 middle dose levels have DLTs in the targeted region

Appendix Table 8. True underlying probabilities of DLT

Scenario	idelalisib	BI 836826		
		100 mg	200 mg	400 mg
1	50 mg BID	0.302	0.436	0.525
	100 mg BID	0.398	0.466	0.563
	150 mg BID	0.428	0.491	0.603
2	50 mg BID	0.092	0.136	0.185
	100 mg BID	0.149	0.257	0.322
	150 mg BID	0.362	0.411	0.441

* Underlined text indicates doses with true probability of DLT within the target toxicity interval [0.20, 0.35)

* Italicized text indicates doses with true probability of DLT within the target toxicity interval [0.35, 1)

Simulation parameters

The metrics evaluated to review operating characteristics are:

- I. Proportion of trials that recommend dose levels with true Pr(DLT) in [20%, 35%) as the MTD (correct decision)
- II. Proportion of trials that recommend dose levels with true Pr(DLT) \geq 35% as the MTD (patient risk)
- III. Proportion of trials that recommend dose levels with true Pr(DLT) $<$ 20% as the MTD
- IV. Proportion of trials which stops early because all dose levels are too toxic
- V. Average number of subjects evaluated

Results of simulation study

[Appendix Table 9](#) summarizes the operating characteristics of the model for the 2 simulated scenarios.

Appendix Table 9. Simulation results for operating characteristics

Scenario	Metrics				
	I	II	III	IV	V
1	14.0%	8.9%	NA	77.1%	9
2	44.0%	12.2%	15.4%	28.4%	19

The probability of recommending a correct dose combination (metric I) shows reasonable performance of BLRM, with 14.0% for Scenario 1 and 44.0% for Scenario 2. The probability of identifying an overly toxic dose combination as MTD (metric II) is low for both scenarios. When most dose combinations are set to overly toxic as in Scenario 1, the chance of stopping the study with identifying the correct MTD or declaring toxicity of all dose levels is high.

In conclusion, the simulations illustrate that the model has reasonable operating characteristics.

4. Simulation Trial Conduction

To help understand the algorithm better, we describe a simulated trial conduct of Scenario 2 with details on DLT observations, posterior distribution, and dose escalation decisions below. Detailed posterior distribution of Pr(DLT) for the candidate combination dose levels are shown for cohort 1 and 2 only to illustrate the algorithm of dose selection. Same algorithm is applied for other cohorts thus not detailed here.

Cohort 1: Three patients were treated at the starting dose of idelalisib 50 mg BID + BI 836826 100 mg (50, 100). None of them experienced a DLT. Let Pr(DLT)_p represent the posterior distribution of Pr(DLT) , BLRM provides probabilities of overdose, on target, and underdose for each combination dose level. There are 5 dose levels satisfying overdose control criterion as listed in the table below. The next dose level to be escalated is (100, 200), which has the highest posterior probability for the target toxicity interval out of all the dose candidates.

Dose Level (idelalisib, BI 836826)	Overdose $\text{Pr(DLT)}_p \geq 35\%$	On Target $35\% > \text{Pr(DLT)}_p \geq 20\%$	Under Dose $\text{Pr(DLT)}_p < 20\%$
100, 200	0.161	0.188	0.651
150, 100	0.221	0.170	0.609
100, 100	0.079	0.158	0.763
50, 200	0.106	0.151	0.743
50, 100	0.031	0.085	0.884

Cohort 2: Three patients were treated at dose level (100, 200), and 1 patient experienced a DLT. BLRM finds the following dose levels satisfying the overdose criterion, and recommends next dose level as (50, 200).

Dose Level (idelalisib, BI 836826)	Overdose $\text{Pr(DLT)}_p \geq 35\%$	On Target $35\% > \text{Pr(DLT)}_p \geq 20\%$	Under Dose $\text{Pr(DLT)}_p < 20\%$
50, 200	0.146	0.245	0.609
100, 100	0.182	0.226	0.592
50, 100	0.047	0.123	0.830

Cohort 3: Three more patients were treated at dose level (50, 200), and no patient experienced a DLT. BLRM recommends dose escalation to (100, 200).

Cohort 4: One DLT was observed in 3 patients treated at dose level (100, 200). BLRM recommends staying at dose level (100, 200).

Cohort 5: No patient experienced DLT, and BLRM recommends dose escalation to (150, 200)

Cohort 6: One DLT was observed, and BLRM recommends dose de-escalation to (100, 200).

Cohort 7: Two DLTs were observed. The algorithm stops as it satisfies the stopping rule. The MTD is claimed as (100, 200).

Appendix Table 10. Simulated Trial of Scenario 2

Cohort	Dose Level (idelalisib, BI 836826)	DLT/ Number of Patients
1	50, 100	0/3
2	100, 200	1/3
3	50, 200	0/3
4	100, 200	1/3
5	100, 200	0/3
6	150, 200	1/3
7	100, 200	2/3

There are safety data available from Study 101-02 in which subjects with previously treated CLL received monotherapy idelalisib ([Appendix Table 11](#)) and from ongoing Phase 1 dose-escalation study 1270.1 in which subjects with R/R CLL received BI 836826 ([Appendix Table 12](#)). Assuming there is no drug-drug interaction, the predicted DLT probabilities of combination doses are summarized in [Appendix Table 13](#).

The proposed priors have higher probabilities of DLT than the predicted ones using historical data at each combination dose level, which means more conservative priors are used for the combination therapy.

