8.11. Sample Size

There is no formal hypothesis to be tested in this study and therefore, no formal sample size calculation is performed. In the Phase 1b portion of the study, a minimum of 3 evaluable subjects will be enrolled in each dose cohort. Approximately 15 subjects are expected to be treated at the highRP2D, including subjects for the expansion cohort. Additionally, approximately 6 evaluable subjects will be treated for the determination of lowRP2D. In total, approximately 42 evaluable subjects are estimated to be enrolled. However, the actual number of subjects will depend on the number of dose cohorts tested.

In the Phase 2 portion of the study, approximately 50 subjects with R/R CLL will be enrolled (20 lowRP2D / 30 highRP2D) .

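### Appendix 6 counts a 77.1% false-stop rate towards good performance; its Table 9 shows a cautious rule, not one shown able to identify a highRP2D

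*Protocol*

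**What the plan says.** All of this is in Protocol Appendix 6.

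- **Target.** The model section defines "Targeted toxicity: [0.20, 0.35"), and a DLT probability of 0.35 or more is excessive.
- **Ending the search.** One of three conditions that end dose finding is "Starting dose level is declared to be too toxic".
- **Scenario.** Section 3 introduces "Scenario 1: Only lowest dose level is safe". Table 8 gives that dose (idelalisib 50 mg BID with BI 836826 100 mg, the starting combination) a true rate of 0.302 and underlines it. The footnote explains: "Underlined text indicates doses with true probability of DLT within the target toxicity interval [0.20, 0.35").
- **Metrics.** Metric I is "Proportion of trials that recommend dose levels with true Pr(DLT) in [20%, 35%) as the MTD (correct decision"). No other metric carries that label. Metric II is recommending a dose at or above 35%, metric III a dose below 20%, and metric IV stopping early because all doses are too toxic.
- **Interpretation.** Below Table 9 the text calls metric I reasonable at 14.0% and 44.0%, and metric II low. It then says that, when most combinations are overly toxic, "the chance of stopping the study with identifying the correct MTD or declaring toxicity of all dose levels is high". It ends: "In conclusion, the simulations illustrate that the model has reasonable operating characteristics".

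**The concern.** Scenario 1 is built so that one dose, the starting dose, is acceptable. A trial that stops because all doses are too toxic has therefore reached a false conclusion. The text adds these stops to the correct selections and presents the total as a strength. The corresponding error in Scenario 2 is not mentioned.

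Establishing the highRP2D is part of the Phase 1b primary objective, and the protocol makes no formal sample-size calculation (Section 8.11). Section 3 is the only place that assesses how often the rule reaches the right answer. A sponsor, Safety Review Team or ethics committee relying on its closing sentence would believe that this ability had been shown, and would not learn how often the rule stops when an acceptable dose exists.

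**Working it through.** **1. Inputs (Tables 8 and 9, as printed; 1000 simulated trials per scenario).**

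| | I correct | II overly toxic MTD | III under-dosed MTD | IV stop, all too toxic | V mean N |
|---|---|---|---|---|---|
| Scenario 1 | 14.0% | 8.9% | NA | 77.1% | 9 |
| Scenario 2 | 44.0% | 12.2% | 15.4% | 28.4% | 19 |

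Each row accounts for all trials: 14.0 + 8.9 + 77.1 = 100, and 44.0 + 12.2 + 15.4 + 28.4 = 100.

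**2. Is metric IV an error?** In Scenario 1 the starting dose is at 0.302 and the other eight combinations run from 0.398 to 0.603. One dose is on target, so a stop is wrong. In Scenario 2 six combinations are below 0.35 (0.092, 0.136, 0.149, 0.185, 0.257, 0.322) and two of these are on target. The starting dose is at 0.092, so a stop is again wrong.

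**3. The pooled figure.** In Scenario 1, I + IV = 14.0 + 77.1 = 91.1%. The false-stop share of that sum is 77.1/91.1 = 85%.

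**4. Counting only metric I as correct.**
- Scenario 1: 14.0% correct; 77.1 + 8.9 = 86.0% incorrect.
- Scenario 2: 44.0% correct; 12.2 + 15.4 + 28.4 = 56.0% incorrect.

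**5. Metric II on both denominators.** Over all trials it is 8.9% and 12.2%. Among trials that recommend a dose it is 8.9/(100 − 77.1) = 8.9/22.9 = 38.9%, and 12.2/(100 − 28.4) = 12.2/71.6 = 17.0%.

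**6. Simulation error.** The 95% half-width at 77.1% is 1.96 × √(0.771 × 0.229/1000) = 2.6 points, too small to matter here.

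**7. Does the written model give Table 9?** The five-parameter model was simulated with the Table 3 priors, cohorts of 3, the 25% overdose criterion, the 100% increment cap and the stated stopping rules. The prior summaries in Table 4 reproduce to within about 0.03 (starting dose: median 0.110 against 0.111, excessive 0.144 against 0.144). Table 9 does not reproduce:
- Scenario 1: I/II/IV = 23.8/18.0/58.2%, mean N 12.
- Scenario 2: I/II/III/IV = 36.2/13.3/45.8/4.7%, mean N 26.

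A second implementation gave stop rates of 54.8% and 4.5%.

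A possible lead: under the written model, one DLT in three at the starting dose gives a posterior probability of excessive toxicity of 0.20, so the dose stays open; two in three gives 0.55 and stops the trial. The chance of at least one DLT in three is 1 − 0.698³ = 66% at 0.302 and 1 − 0.908³ = 25% at 0.092. The printed stop rates look closer to a rule that stops on a single early DLT. Reading the prior variance of 2 as a standard deviation gives stop rates of 78.2% and 25.0%; a 20% overdose cut-off gives 76.6% and 25.1%. Neither variant reproduces the rest of Scenario 2 (metric I 29.0% or 24.7% against 44.0%; metric III 39.6% or 42.4% against 15.4%).

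**The case against.** - **Stopping is the cautious error.** Overdose control is the stated design criterion, 0.302 is near the top of the target interval, and eight of nine combinations in Scenario 1 are too toxic. This stands. It is a reason to describe a trade-off, not to count the error with the successes.
- **No threshold for reasonable is set.** The pooled sentence is arithmetically true, and 77.1% is printed just above it. This also stands. A reader might infer that the conclusion is simply wrong; the documents support only that Table 9 does not back it.
- **Comparison with chance.** A reader might set 14.0% against a random choice among nine combinations (1/9 = 11.1%) and infer that the rule hardly beats chance. That ignores patient risk: a random choice would be overly toxic in 8/9 = 88.9% and 3/9 = 33.3% of trials, against 8.9% and 12.2% in Table 9.
- **Information in a stop.** A reader might infer that a toxicity stop says almost nothing. Table 9 contradicts this: stops occur in 77.1% of trials at a true starting rate of 0.302 and in 28.4% at 0.092. What cannot be judged is whether a stop separates an on-target starting dose from one at or above 35%, because no scenario with every dose that toxic was run.
- **Other support.** Appendix 6 also gives prior summaries, monotherapy data and one worked trial, and the Safety Review Team weighs other safety and PK data. None of these measures how often the rule is right.
- **The study is over.** Protocol Section 1.4 says that no highRP2D will be determined, and SAP Section 7.6 says that DLTs will not be evaluated. This lowers the priority; the current protocol still carries the claim.

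**Conclusion.** The concern holds as a point about interpretation. On Table 9 as printed, the rule is correct in 14.0% and 44.0% of trials and stops falsely in 77.1% and 28.4%. The table shows protection against recommending an overly toxic dose, but it does not show the ability to identify a highRP2D that the conclusion implies.

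This rests on the printed figures and on the appendix's own definition of a correct decision. The Scenario 1 point also survives under the written model, where about 55–58% of trials stop falsely. The Scenario 2 point depends on the printed 28.4%, since the written model gives about 5%. The overdose protection in Scenario 1 is likewise weaker in that simulation (metric II 18.0% against 8.9%).

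A reader might infer from step 7 that Table 9 is in error. That is not established: the cohort size simulated and the choice of MTD at 36 subjects are not stated. It is a reason to check the table. Practical consequence is small, because the study ended with 2 subjects.

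**What to change.** In Appendix 6, Section 3:

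1. Verify or re-run Table 9 against the model as written, and state the simulation settings used.
2. Label metric IV as a false stop in both scenarios.
3. Delete the sentence that pools it with correct MTD identification.
4. Replace the conclusion with the separate rates, once verified. As printed they are: correct 14.0% and 44.0%; false stop 77.1% and 28.4%; overly toxic MTD 8.9% and 12.2% of all trials, or 38.9% and 17.0% of trials that recommend a dose. Describe the rule as cautious with a high false-stop rate, if the verified figures still show one.
5. State that no scenario with every dose at or above 35% was simulated, so the table cannot show whether a toxicity stop separates an on-target starting dose from one at or above 35%. Adding such a scenario is optional.

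The cost is a short text edit and one simulation check, with no effect on subjects or procedures; the stated performance will look less favourable. Whether the dose-finding rule itself changes is for the sponsor and the Safety Review Team. With the study terminated, this is a low-priority correction, mainly useful if the appendix is cited or reused.

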Appendix Table 11. Summary of DLTs* from monotherapy idelalisib study

Dose of idelalisib	No of DLTs/No of evaluable subjects
100 mg BID	3/11
150 mg BID	8/52
200 mg BID	3/10
350 mg BID	3/7

* Number of DLTs is retrospectively re-calculated using the definition of DLT in Study GS-US-312-1579

Appendix Table 12. Summary of DLTs from monotherapy BI 836826 study

Dose of BI 836826	No of DLTs/No of evaluable subjects
1 mg	0/3
3 mg	0/3
9 mg	0/6
25 mg	0/6
50 mg	0/3
100 mg	0/3
200 mg	1/6
400 mg	0/3
800 mg	1/2

Appendix Table 13. Summary of DLTs predicted from monotherapy of Idelalisib and BI 836826

Dose level		Pr(DLT)
Idelalisib	BI 836826	Median
50 mg BID	100 mg	0.107
100 mg BID	100 mg	0.169
150 mg BID	100 mg	0.222
50 mg BID	200 mg	0.152
100 mg BID	200 mg	0.211
150 mg BID	200 mg	0.261
50 mg BID	400 mg	0.259
100 mg BID	400 mg	0.311
150 mg BID	400 mg	0.355
50 mg BID	800 mg	0.459
100 mg BID	800 mg	0.497
150 mg BID	800 mg	0.529

## LIST OF ABBREVIATIONS

AE	adverse event
ALP	alkaline phosphatase
ALT	alanine aminotransferase
AST	aspartate aminotransferase
BID	twice daily
BLQ	below the limit of quantitation
BLRM	Bayesian logistic regression analysis
BMI	body mass index
CLL	chronic lymphocytic leukemia
CR	complete response
CSR	clinical study report
CTCAE	Common Terminology Criteria for Adverse Events
DCR	duration of complete response
DLT	dose limiting toxicity
DMC	data monitoring committee
DOE	duration of response
DSPH	Drug Safety and Public Health
ECG	electrocardiogram
ECOG	Eastern Cooperative Oncology Group
eCRF	electronic case report form
highRP2D	high recommended Phase 2 dose
HLGT	high-level group term
HLT	high-level term
IV	intravenous
LLT	lower-level term
LOQ	limit of quantitation
lowRP2D	low recommended Phase 2 dose
MedDRA	Medical Dictionary for Regulatory Activities
MRD	minimal residual disease
n	number of subjects
ORR	overall response rate
OS	overall survival
PFS	progression-free survival
PT	preferred term
Q1, Q3	first quartile, third quartile
QRS	electrocardiographic deflection between the beginning of the Q wave and termination of the S wave representing time for ventricular depolarization

---

QT	electrocardiographic interval between the beginning of the Q wave and termination of the T wave representing the time for both ventricular depolarization and repolarization to occur
R/R	relapsed/refractory
SAE	serious adverse event
SAP	statistical analysis plan
SE	standard error
SOC	system organ class
SRT	Safety Review Team
StD	standard deviation
TEAE	treatment-emergent adverse event
TFs	tables, figures, and listings
ULN	upper limit of normal

